10.2 Target sample size

We project to reach 1,200 female youth over an accrual period of up to 12 months, plus one year of follow-up. Therefore, in order to stay within the estimate 12 months of recruitment, we will put in place adequate field staff during the implementation phase of the project.

Because Aim 1 of this study is not a clinical trial, but rather an exploration of differences in the yield of previously undiagnosed HIV infection across recruitment and testing strategies, we started with this large and feasible sample size and conducted power calculations to determine the size of effects detectable with at least 80% power. By recruiting 1200 female youth between the age of 15-24 years, we will have 80% power to detect an odds ratio of 1.67 when comparing recruitment strategies, on the proportion of previously undiagnosed female youth testing positive for HIV infection. And when comparing testing approaches within a recruitment strategy on that same outcome, an odds ratio of 2.01 can be detected with 80% power. These calculations, which are presented in more detail in section 15.11, show the proposed sample size (N=1200) is capable of detecting modest differences in the yield of previously undiagnosed HIV infection across both recruitment strategies and testing approaches.

We expect large numbers of youth to participate through both venues (IRDO reaches tens of 1000s of youth/year). Based on our experience with MP3 Youth (data not yet published) study (KNH/UON ERC P23/03/2011), which screened N=788 female youth and enrolled N= 690 female youth over a period of 8 months (November 19, 2014 – June 12, 2015) in the same county, we anticipate that we will be able to recruit 1,200 females over a period of 12 months with enhanced recruitment effort. We expect the sample accrual rate to be slower than in MP3 Youth, because we will be recruiting only female youth and mainly those out of school (a large proportion of younger MP3 Youth girls were in school and easier to recruit). In addition, we have two different recruitment strategies, and the home-based strategy may be more labor intensive and time consuming than a community mobile event. We therefore expect a somewhat lower accrual rate.

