Logistic regression analysis will be used to determine which recruitment and HIV testing approaches yield the highest proportion of newly diagnosed HIV infection. HIV testing result (negative vs. positive) will be regressed on variables indicating recruitment strategy (home vs. community) and type of HIV testing (self, staff-aided, facility-based). With facility-based testing following community-based recruitment as a reference category, we will estimate how home-based recruitment and other testing approaches change the odds of a positive test result. The interaction between recruitment strategy and HIV testing approach will be tested to determine whether the yield of each testing approach is conditional on recruitment strategy. If a significant interaction effect is found, simple main effects of testing approach within each recruitment strategy and simple main effects of recruitment strategy within each testing approach will be estimated. In addition to comparing yield by recruitment strategies and testing approaches, we will consider interaction effects with youth characteristics, such as age, risk behaviors, and HIV testing history, and type of testing. Similar logistic regression analyses will examine differences in the odds of completing all confirmatory testing by recruitment strategy and approach to testing.

Home-based and community-based recruitment strategies will also be compared to determine which strategy is more effective in reaching higher risk female youth. Rates of acceptance of screening among potential participants offered screening and rates of enrollment among eligible participants will be compared by recruitment strategy using logistic regression. Risk will be characterized by number and serostatus of sex partners, concurrency, condom use, and patterns of HIV testing by the participant and any sex partners.

A random selection of N≈185 girls with HIV negative tests will be followed-up. We will assess risk behaviors, condom use, additional HIV testing, linkage to prevention and any new HIV diagnoses over the year since study enrollment. Re-testing, prevention service use, and new HIV will be examined in relation to recruitment strategy, testing approach at enrollment, and participant risk behavior and other characteristics.

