15.11 Sample Size Considerations

Baseline sample size calculation

Based on our experience with MP3 Youth (data not yet published), which screened N=788 female youth and enrolled N=690 female youth over a period of eight months (November 19, 2014 – June 12, 2015), we expect we can recruit N=1200 female youth over a period of around twice that time. We expect the sample accrual rate to be slower than in MP3 Youth, because we will be recruiting only female youth and mainly those out of school (a large proportion of younger MP3 Youth girls were in school and easier to recruit). In addition, we have two different recruitment strategies, and the home-based strategy may be more labor intensive and time consuming than a community mobile event. We therefore expect a somewhat lower accrual rate. Therefore, in order to stay within the estimate 12 months of recruitment, we will increase our field staff during the implementation phase of the project. Sample size estimates are also based on IRDO's program data and the estimated number of youth in Homa Bay. We expect large numbers of youth will be successfully recruited from the home and mobile events (IRDO reaches tens of thousands of youth/year) for a total sample size of ≥ 1200 female youth.

Power Analysis

Power calculations for Aim 1 are based on the yield of newly diagnosed HIV across recruitment strategies and testing options offered to female youth. Using version 12 of the PASS program (Hintze, 2013) for logistic regression, we did not approach this power analysis from the perspective of calculating a sample size needed to detect a particular effect size with at least 80% power. Rather, because this part of the study (Aim 1) is not a clinical trial but rather an exploration of preferences and yield of recruitment and participant-selected testing strategies, we started with the large, feasible sample size and determined the size of effects that could be detected with at least 80% power when comparing recruitment strategies and HIV testing approaches.

The expected percentage of girls testing positive is based on our MP3 Youth pilot study. In that study, 55 of 636 female youth not previously diagnosed were found to have HIV infection (data not yet published). Thus, we expect about 9% of all tested females in this study to have HIV infection not previously diagnosed.

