With this estimate of the expected percentage of girls with newly diagnosed HIV infection, we asked how small of an increase in the odds of newly diagnosed HIV infection could be detected with 80% power when community-based recruitment is compared to home-based recruitment. With 600 youth recruited by each strategy, power is 80% to detect an odds ratio of 1.67, in other words, a modest increase from 9% to 14% newly diagnosed with HIV infection. When comparing testing approaches, and assuming an equal proportion of girls prefers each approach and testing approach does not interact with recruitment strategy, power is 80% to detect an odds ratio of 1.85. If there is an interaction between recruitment strategy and testing approach, when comparing

testing approaches within a recruitment strategy (i.e., estimating simple main effects), power is 80% to detect an odds ratio of 2.32.

These calculations show the proposed sample size (N=1200) is capable of detecting modest differences in the yield of newly diagnosed HIV infection across both recruitment strategies and testing approaches.

Among the approximately 108 female youth we expect to be newly diagnosed with HIV infection, about 20% are expected to successfully initiate HIV care at a health facility after a single SMS message. The remaining 80% (N=86) who are not linked to care after the initial SMS message will be randomly assigned to either continued SMS messages or to economic incentives. Assuming at least 60% are linked to care at some point during follow-up, survival analysis employing Cox regression will be able to detect a hazard ratio of 2.2 describing the impact of treatment condition (continued SMS vs. economic incentives) on the occurrence and timing of successful linkage to care at a health facility, with 80% power.

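### The 80% power at OR 2.32 for comparing testing approaches within a recruitment strategy leaves out the interaction test that must be passed first

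*Combined protocol and SAP*

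**What the plan says.** Section 13.2 (Statistical Analyses) fits a logistic regression of test result on recruitment strategy and testing approach, and adds an interaction: "The interaction between recruitment strategy and HIV testing approach will be tested to determine whether the yield of each testing approach is conditional on recruitment" (last word omitted). The next step depends on the result: "If a significant interaction effect is found, simple main effects of testing approach within each recruitment strategy", and of recruitment strategy within each testing approach, are to be estimated. Neither 13.2 nor Table 1 describes another route to the within-strategy estimates.

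Section 15.11 (Power Analysis) treats the same comparisons. It begins "If there is an interaction between recruitment strategy and testing approach, when comparing" and continues "testing approaches within a recruitment strategy (i.e., estimating simple main effects), power is 80% to detect an odds ratio of 2.32". It gives no power for the interaction test and no size or shape for the interaction.

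Section 10.2 gives another figure for the within-strategy comparison, without the interaction condition: "an odds ratio of 2.01 can be detected with 80% power".

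**The concern.** A comparison that is made only after a significant interaction cannot be more powerful, as a procedure, than the interaction test that opens the way to it. Interaction tests are usually much weaker than simple-effect tests on the same cells. If the 80% takes no account of that step, the plan claims a property that its own analysis rule does not have.

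At stake is whether a real difference between testing approaches in one venue would be reported as such. Sections 10.2 and 15.11 both use these figures to conclude that 1,200 participants can detect modest differences in yield across testing approaches.

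**Working it through.** **Inputs**
- Base rate 9%. Section 15.11: "we expect about 9% of all tested females in this study to have HIV infection not previously diagnosed" (55/636 = 8.65%).
- 600 per recruitment strategy. Section 15.11: "With 600 youth recruited by each strategy, power is 80% to detect an odds ratio of 1.67".
- Equal thirds, so 600/3 = 200 per approach within a strategy. Section 15.11 states the equal split for the pooled comparison ("assuming an equal proportion of girls prefers each approach"); I carry it over to the within-strategy one.
- Alpha and sidedness are not stated. I assume 0.05 two-sided, for the simple effect and for the gate.
- The odds ratio in the other venue is not stated, so I vary it.

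**Step 1: reproduce the plan's figure**

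p2 = OR·p1/(1 − p1 + OR·p1) = 2.32 × 0.09/(0.91 + 0.2088) = 0.1866; mean rate 0.1383.

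Power = Φ{[(p2 − p1) − 1.96·√(2·p̄(1 − p̄)/n)] / √([p1(1 − p1) + p2(1 − p2)]/n)}
= Φ{[0.0966 − 1.96 × 0.0345]/0.0342} = Φ(0.85) = 80.2%.

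The same formula gives 80.1% at OR 1.67 with 600 per group and 79.8% at OR 1.85 with 400. All three figures in 15.11 reproduce, so the 80% at OR 2.32 is the power of one ungated comparison of 200 with 200.

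**Step 2: add the gate**

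I simulated the 2 × 3 layout with 200 per cell (40,000 to 60,000 runs per case). The gate is a 2-df likelihood-ratio interaction test at 5%. Success means that the gate is passed and the OR 2.32 contrast is significant at 5%. One approach has OR 2.32 in one venue, and every cell not named is at 9%. Ungated, the simple effect is significant in 81% of runs throughout.

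| OR for that approach in the other venue | Gate passed | Gate passed and simple effect significant |
|---|---|---|
| 1.0 | 48% | 44% |
| 1.25 | 29% | 28% |
| 1.5 | 17% | 16% |
| 1.75 | 10% | 9% |
| 2.0 | 7% | 6% |
| 0.75 | 71% | 63% |
| 0.43 (= 1/2.32) | 94% | 78–79% |

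At OR 1.52 in the other venue the joint figure is 15%. If both non-reference approaches have OR 2.32 in one venue and the other venue is null, it is 40%. With the gate relaxed to 10%, the first three rows become 55%, 38% and 25%.

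**Step 3: closed-form check on the interaction**

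For a one-df contrast with the other venue null:
SE = √[3/(200 × 0.09 × 0.91) + 1/(200 × 0.1866 × 0.8134)] = √(0.1832 + 0.0329) = 0.465.
Power = Φ(ln 2.32/0.465 − 1.96) = Φ(0.842/0.465 − 1.96) = 44%.
At OR 1.25 and 1.5 in the other venue the same calculation gives 28% and 16%.

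For 80% power the ratio of odds ratios R must satisfy ln R = 2.80 × SE(R). At R = 3.60 the elevated cell has rate 0.2625, SE = 0.457, and 2.80 × 0.457 = 1.28 = ln 3.60. So a ratio of about 3.6 is needed.

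**Step 4: what remains when the gate fails**

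The pooled testing effect is still estimated. With OR 2.32 in one venue and 1.0 in the other, the variances of the two log odds ratios are 1/16.38 + 1/30.36 = 0.0940 and 2/16.38 = 0.1221. The weighted log odds ratio is (0.842/0.0940)/(1/0.0940 + 1/0.1221) = 0.476, a pooled OR of about 1.6.

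**Step 5: the figure in 10.2**

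At OR 2.01, p2 = 0.1658, and the Step 1 formula with 200 per group gives 62%. It takes about 304 per group to reach 80%.

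**The case against.** **The 80% is stated for the case where an interaction exists.** That is so, and as the power of that single comparison it is correct. A reader might infer that 80% is a miscalculation; the documents do not support that. Given a passed gate, power is even higher, about 82 to 95% in the scenarios with a true difference between venues. But 15.11 supposes that an interaction exists, not that it is detected. Every row of the table contains a true interaction, and the joint chance is still mostly well below 80%.

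**The primary aim does not depend on these comparisons.** This stands in part. A reader might infer that the primary objective asks for the best testing approach within each venue. Sections 6, 8 and 13.1 ask for the preferred venue and the preferred modality. The overall comparisons are powered separately (OR 1.67 and 1.85) and are not gated. The within-venue contrasts are a follow-up, but one for which the plan claims power.

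**The signal is not lost when the gate fails.** Largely right. Counting a significant pooled effect as a detection, some testing effect is found in about 74 to 85% of runs for other-venue odds ratios of 1.0 to 1.5. When both venues point the same way, the pooled estimate is a fair summary. A reader might infer that it conceals the effect; it dilutes it. It is, however, a different quantity from the within-strategy odds ratio to which the power statement refers.

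**Aim 1 is declared exploratory, and following up an interaction test is conventional.** Both are true and lower the severity. An exploratory purpose also favours estimates with intervals over a significance gate.

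**Conclusion.** The concern holds in limited form. The 80% at OR 2.32 in 15.11 is right for one ungated comparison but is not the power of the procedure in 13.2, and the plan gives no power for the step in between.

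The size depends on assumptions that the documents do not supply: a 2-df gate at 5%, equal cells of 200, and the odds ratio in the other venue. Under the first two, the chance of reaching and finding OR 2.32 in one venue is about 44% with a null other venue, 28% at OR 1.25 and 15 to 16% at OR 1.5. The range 15 to 44% should not be read as a general result: the chance falls below 10% when the venues are closer and reaches about 78 to 80% for a full crossover.

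The interaction test should not be made to look weaker than it is. Putting the 9% variance in all four cells gives a required ratio of odds ratios of 3.99; with the proper variance for the elevated cell it is about 3.6.

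Separately, and without any of the gate assumptions, OR 2.01 in 10.2 and OR 2.32 in 15.11 cannot both be the detectable effect for the same comparison.

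**What to change.** In 13.2, replace the conditional step with a commitment always to report the six venue-by-approach yields and the within-venue odds ratios with 95% confidence intervals. Label them exploratory and unadjusted for multiplicity, and report the interaction test alongside. The model with interaction terms already contains these estimates, so no new data are needed. If an adjustment is preferred, say so and restate the power: Bonferroni for three pairs (critical value 2.39) gives about 66% at OR 2.32.

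If the gate is kept, state in 15.11 that the 80% excludes the chance of passing it. Give the level of the gate and the power of the two-step procedure under a stated odds ratio in the other venue.

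In either case, correct OR 2.01 in 10.2 so that it agrees with 15.11.

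The cost is a few sentences. The downside is small: more intervals are reported, and if the gate is kept the stated power becomes less favourable.

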11.5.1 HIV Testing Services, POC CD4 Testing, and Viral Load Testing

- HTS sample target N=1200.

Whether recruited in the home or in the community, after an individual has been consented, screened for eligibility and registered to participate in the GIRLS study, they will be offered three

HIV testing options: staff-aided testing, self-testing, and referral to standard facility based HTS. The current government of Kenya HTS testing guidelines will be followed in all the cases. The government of Kenya has set standards on HIV self-testing (NASCOP, 2015), and we will follow these guidelines.

Staff-aided testing

The participant will receive:

- Pre-test counseling,
- HIV testing per GoK guidelines,
- Post-test counseling,
- PIMA-CD4 POC assay and viral load test (if positive),
- Referral to services if applicable.

This HTS process is based on the Kenyan National guidelines on rapid HIV testing; most recently updated August 2015 (See Appendix G).

- Participants will undertake a screening rapid test. If positive a confirmatory test will be administered. A third rapid tie breaker will be done to confirm discordant results. This testing will be done sequentially by staff in the home or mobile setting.
- Those who test negative will be reported as HIV negative.
- Those who test positive on two rapid tests will be reported as HIV positive.

For an individual who has an HIV positive test result, the CD4 and viral load samples will be taken immediately on site. The CD4 results will be communicated and the printout will be given to the participant. The viral load sample will be done using dried blood spot (DBS) which we have done successfully in our other studies through the CDC Kenya lab (Inzaule et al., 2013). The viral load results will be communicated after 2 weeks when the results are received from the lab. The HTS intervention will last approximately 35-45 minutes depending on the participant's level of knowledge and engagement during the pre and post counseling sessions.

Self-testing

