If the participant does not page the number within a 2-week period, the RA will contact them by phone. If they still do not respond, we will trace them using the locator information provided at enrollment. For participants with a positive or indeterminate self-test result, the RA will ascertain a convenient location for conducting the confirmatory test in accordance with current government of Kenya HTS rapid testing algorithm. This may include home based or community, in line with the current recruitment strategy, or at a health care facility. Additionally, a randomly selected proportion (10%) of participants with a negative result will also undergo confirmatory testing for QA/QC purposes per current GoK HIV testing guidelines (NASCOP, 2015). Study staff will be trained and enrolled in the proficiency panel testing QA program with the MoH. When a participant requires confirmatory testing, the RA will follow the standard HTS guidelines for rapid HIV testing, which includes conducting two rapid tests and a tie-breaker if the results are discrepant. At this point if the HIV test is positive, CD4 and VL will be collected and the individual will be invited to enroll in the linkage intervention.

Standard facility based HTS

We will be working with Homa Bay County, Ndhiwa and Mbita health facilities. Participants who choose to test via standard facility based HTS will be given a card with the name of a research assistant/contact person at the facility. Additionally, the participant's detailed locator information will be collected to ensure we can follow up with them as needed. HTS procedures will be conducted per Government of Kenya guidelines. If the participant tests positive, they will be invited to enroll in the linkage intervention.

POC CD4 Testing

At a mobile event, in the home, or facility, if a participant is confirmed positive for HIV, a portable PIMA CD4 analyzer (Alere, Inc., Waltham, Massachusetts, USA) will be used for a Point of Care (POC) CD4 count (Mwau et al., 2013). A finger stick specimen will be taken using an aseptic technique and processed in the PIMA analyzer. Results will be given verbally and in writing to the participant. The results will be used in the counseling for HIV-1 positives. Although WHO new Test and START guidelines recommends immediate treatment irrespective of CD4 count (WHO, 2015), we will collect CD4 at baseline for clinical staging, counseling and treatment preparation purposes.

Viral Load Testing

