13.2 Description of the Analyses

See Table 1: Evaluation Plan for Data Management and Analysis.

Baseline Data

1. Basic demographic information
2. Sexual risk behaviors
3. HIV risk behaviors
4. Attitudes/knowledge about HIV transmission and prevalence
5. Knowledge and acceptability of specific HIV prevention interventions

6. Knowledge and acceptability of family planning methods

The primary endpoint for comparisons of recruitment and testing strategies is newly diagnosed HIV infection. The key outcomes we detail below are broken out by study aims and based on the HIV prevention and treatment continua, which organizes our outcomes of interest by recruitment strategies, testing, linkage, retention and primary prevention.

Primary Endpoints

Primary outcomes of interest for Aim 1 is based on the HIV prevention and treatment continua as outlined below:

- Recruitment/Seek: Ability to identify and recruit female youths that are high risk for HIV infection using two seek strategies (home-based vs. community-based)
 - The proportion of youth in the community who accept study screening (estimated from total youth approached as the denominator);
 - The proportion of youth who accept study enrollment (estimated from youth screened and eligible as the denominator).
- Testing:
 - Testing uptake by different testing modalities;
 - Completion of confirmatory testing;
 - Proportion that are positive;
 - Among those who are positive, completion of baseline collection of CD4 and viral load tests.

Outcomes of interest for the Aim 3 economic evaluation include:

- Compute the cost per HIV-infected female youth identified under each 'seek' strategy (home-based vs. community based);
- Compute the cost per HIV-infected female youth identified under each 'test' strategy (self-testing, staff delivered HTS testing, standard facility-based HTS);
- Calculate the incremental cost-effectiveness ratio of the adaptive linkage to care intervention among HIV positive female youth;
- Compute the cost of the SMS prevention intervention among HIV negative female youth.

Secondary Endpoints

- Linkage to Care:
 - Percent of females who tested positive that attended a first HIV care appointment at an HIV Comprehensive Care Center (CCC)
 - Time to link to care after positive confirmatory test result
- Retention in Care:
 - Completion of viral load testing at 12 months;
 - Reported appointment attendance via SMS and verification by study staff at 3, 6, 9, and 12 months.

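### Completion of confirmatory testing has no stated denominator and covers different events by testing approach, so the planned ordinary logistic regression may not give usable odds ratios

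*Combined protocol and SAP*

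**What the plan says.** Sections 6 and 13.2 list "Completion of confirmatory testing" among the Aim 1 testing outcomes. Neither they nor Table 1 say who is due a confirmatory test or by when. Neighbouring outcomes are better defined. The screening and enrollment proportions have stated denominators, and the CD4/viral load item reads "Among those who are positive, completion of baseline collection of CD4 and viral load tests".

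The planned analysis, which follows the yield model in Section 13.2, is: "Similar logistic regression analyses will examine differences in the odds of completing all confirmatory testing by recruitment strategy and approach to testing". The yield model takes facility testing after community recruitment as its reference.

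Section 11.5.1 describes confirmation differently for each approach:

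- **Staff-aided:** a screening test, a confirmatory test if positive, and a tie-breaker if discordant. "This testing will be done sequentially by staff in the home or mobile setting". The whole service is put at 35 to 45 minutes.
- **Facility:** "HTS procedures will be conducted per Government of Kenya guidelines", and for every approach, "The current government of Kenya HTS testing guidelines will be followed in all the cases". Same-visit confirmation is not stated in words.
- **Self-test, positive or indeterminate:** the girl tests alone within 2 weeks; afterwards "the RA will ascertain a convenient location for conducting the confirmatory test".
- **Self-test, negative:** "Additionally, a randomly selected proportion (10%) of participants with a negative result will also undergo confirmatory testing for QA/QC purposes". Section 14.1 repeats this rule for self-test negatives. For blood-based testing it describes proficiency panels and specimen checks, not a second test of the participant.

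The costing text in Section 13.2 attaches the confirmatory-test cost in the self-test group to girls whose self-test was positive.

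**The concern.** The same term names three things: a step inside a testing session, a return contact after a reactive self-test, and a QA re-test of girls who tested negative. Without a denominator, two analysts could follow the text and report different results for the same outcome.

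What is at stake is how many girls are lost between a reactive self-test and a diagnosis. That bears on whether self-testing works as a route into care. A denominator that includes QA negatives blurs this figure. A denominator of everyone tested largely turns the outcome into positivity. The sensible denominator, girls with a reactive first test, leaves small cells with few or no failures in at least one approach, where ordinary logistic regression behaves badly.

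**Working it through.** **The plan's own figures.** The plan gives no sample size or power figure for this outcome. Its Aim 1 power concerns yield: 600 per strategy, 9% base rate, odds ratio 1.67. Here p2 = 0.09 × 1.67 / (1 − 0.09 + 0.09 × 1.67) = 0.142. The two-proportion normal approximation at two-sided 5% (assumed, not stated) gives 80.05% power, matching the stated 80%. The expected count also reproduces: 1200 × 0.09 = 108.

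**Inputs.** 9% newly diagnosed and equal thirds across approaches (Section 15.11); 10% QA sampling of self-test negatives (Section 11.5.1). Completion rates below are assumptions, shown as ranges.

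**1. Make-up of the self-test denominator, read literally.**
- Self-testers: 1200 / 3 = 400.
- Positives: 400 × 0.09 = 36.
- QA negatives: (400 − 36) × 0.10 = 36.4.
- QA share: 36.4 / 72.4 = 50.3%.
- The share does not depend on how many choose self-testing: 0.091 / (0.09 + 0.091) = 50.3%.

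This is approximate. It treats the 9% newly diagnosed as the reactive proportion and ignores false-reactive or indeterminate results and unreturned kits.

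**2. Effect of pooling.** Pooled completion = (36 × c₁ + 36.4 × c₂) / 72.4, with c₁ for positives and c₂ for QA negatives.

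| c₁ | c₂ | Pooled | Pooled odds ÷ positives-only odds |
|---|---|---|---|
| 70% | 50% | 59.9% | 0.64 |
| 70% | 100% | 85.1% | 2.44 |
| 90% | 50% | 69.9% | 0.26 |
| 90% | 100% | 95.0% | 2.12 |

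The error can go either way, depending on whether QA girls complete more or less often than positives.

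**3. Denominator of everyone tested.** If all 36 staff-tested positives complete, the staff figure is 36 / 400 = 9.0%. For self-testing at 70% to 90% completion it is 36 × 0.70 / 400 = 6.3% to 36 × 0.90 / 400 = 8.1%. The result then mainly tracks positivity.

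**4. Denominator of girls with a reactive first test.** This leaves 108 / 3 = 36 per approach and 108 / 6 = 18 per approach-by-strategy cell. The chance that nobody fails in a group is (true completion)ⁿ:

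| True completion | n = 36 | n = 18 |
|---|---|---|
| 95% | 16% | 40% |
| 98% | 48% | 70% |
| 99% | 70% | 83% |

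A group with no failures has no finite maximum-likelihood log-odds. For a whole approach (36) this affects a main-effects model; for a single cell (18) it affects the interaction model. The exact 95% interval remains available: its lower limit is 0.025^(1/36) = 90.3% for 36/36 and 0.025^(1/18) = 81.5% for 18/18.

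**The case against.** The strongest reply is that this is a wording gap.

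- **QA inclusion is not stated.** The re-test of negatives is labelled QA, and the costing text ties self-test confirmation to positive results. The team may always have meant positives only. This stands as far as it goes, but the regression sentence refers to all confirmatory testing, and nothing excludes the QA girls.
- **Facility confirmation is inferred.** The sequential procedure is stated only for staff in the home or mobile setting. Appendix G gives the order of the kits, not same-visit completion. Facility choosers must also attend for their first test, so if the denominator were everyone choosing that approach, completion could be far from 100%. This stands. Near-complete confirmation is well supported for staff-aided testing only.
- **Separation is a risk, not a certainty.** At 95% true completion, a cell of 18 has a 40% chance of no failures. Contrasts that avoid the empty group, such as home against community among self-testers, may remain estimable. This stands.
- **The separate self-test appointment is real.** The study compares strategies as they would be used, so lower completion after self-testing is a consequence worth estimating. This also stands.
- **The outcome is not the main one.** Section 13.2 names newly diagnosed infection as the primary endpoint for comparing strategies, and Section 15.11 calls Aim 1 exploratory.

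These replies limit the point but do not supply a denominator, or a method for groups with almost no failures.

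**Conclusion.** The outcome is under-defined, and the named method is poorly suited to the denominator that makes most sense. On the literal wording, QA negatives could form about half of the self-test denominator. On a reactive-only denominator, about 36 girls per approach and 18 per cell remain, and an approach with 98% to 99% true completion has a 48% to 70% chance of no failures. These figures rest on 9% positivity, equal thirds and the assumed completion rates.

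A reader might infer four stronger things that the documents do not support:

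- that self-test completion will be overstated: QA inclusion is permitted but not stated, and the shift can go in either direction;
- that facility completion is 100% by design: this is an inference from national guidelines;
- that the odds ratios cannot be estimated: they may well not be, which is a matter of probability;
- that the comparison by approach is invalid because self-testers need another appointment: that is part of the strategy, and the comparison may stay.

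The point merits a change to the analysis text. It does not touch the primary endpoint of newly diagnosed infection.

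**What to change.** - Define the endpoint as completion of the national testing algorithm, within a stated window, among girls with a reactive or indeterminate first test, for every approach. State alongside it how many self-testers never had a result returned.
- Report the 10% QA sample of self-test negatives separately, as agreement between self-test and algorithm result.
- Give completion by approach, and by approach within recruitment strategy, as counts with exact intervals.
- For any comparison by approach or recruitment strategy, pre-specify exact or penalised logistic regression.
- In self-testers, report time from self-test to confirmatory result. Section 11.7.1 records the date the kit was dispensed; the text does not say that the date of the self-test is captured, so this should be checked.

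The cost is endpoint and analysis wording, plus possibly one date field. The downside is that the self-test figure may look less favourable and the intervals will be wide, with about 18 girls per cell.
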